## 8.2 PHARMACOKINETICS AND IMMUNOGENICITY DEFINITIONS AND ENDPOINTS

### 8.2.1 PHARMACOKINETICS

- PK will be evaluated by non-compartmental analysis (NCA). The table below defines the PK parameters that maybe derived from the NCA for this study.

Parameter Abbreviation	Definition	Unit	Dependence on $\lambda_z$
$C_{\max}$	Maximum observed plasma concentration	ng/mL	no
$T_{\max}$	Time when $C_{\max}$ is observed	days	no
$AUC_{\text{last}}$	Area under the drug concentration-time curve from time 0 to the time of the last quantifiable drug concentration	ng·days/mL	no
$AUC_{\text{inf}}$	Area under drug concentration curve from time 0 extrapolated to infinity	ng·days/mL	yes
$\lambda_z$	Terminal elimination rate constant	days 	NA
$t_{1/2}$	Terminal elimination half-life	days	yes
CL	Clearance of drug	L/day	yes
$V_d$	Volume of distribution	L	yes
$C_{\max}/D$	$C_{\max}$ normalized by dose	ng/mL/mg	no

AUC last /D	AUC last normalized by dose	ng·days/mL/ mg	no
AUC inf /D	AUC inf normalized by dose	ng·days/mL/ mg	yes

Parameters with no dependence on  $\lambda_z$  will be calculated for all subjects. Parameters with a dependence on  $\lambda_z$  will be calculated and reported as described in Section 9.10 Pharmacokinetic and Immunogenicity Analyses.

### 8.2.2 IMMUNOGENICITY

Immunogenicity endpoints include ADA and NAb incidence.

## 8.3 EFFICACY DEFINITIONS AND ENDPOINTS

### 8.3.1 RECISTv1.1

For solid tumors, investigators will evaluate the size of the tumor based on a set of published guidelines called Response Evaluation Criteria in Solid Tumors (RECIST). The current set of guidelines are referred to as RECISTv1.1 (Eisenhauer, et al., 2009). Tumor evaluations are based on Target and Non-Target lesions plus new lesions potentially occurring post dose at subsequent assessments.

Measurable lesions will include nodal and non-nodal as follows: 1) lesions with longest diameter 10mm or greater in the axial plane when assessed by CT or MRI, 2) lesions with the longest diameter at least 20 mm with assessed by chest x-ray 3) superficial lesions with longest diameter 10 mm or greater when assessed by caliper 4) malignant lymph nodes with the short axis 15 mm or greater when assessed by CT. RECIST recommends contiguous slice thickness of less than or equal to 5mm for CT or MRI. Nodes with a short axis less than 10mm should not be considered malignant lesions. Ultrasound is not suitable for tumor assessment.

Non-measurable lesion categorization will include all other diseases including lesions too small to be considered measurable, pleural or pericardial effusions, ascites, bone disease, inflammatory breast disease, leptomeningeal disease, lymphangitis, pulmonitis, clinical lesions that cannot be accurately measured with calipers, abdominal masses identified by physical exam that are not measurable by reproducible imaging, nodes with short axis greater than or equal to 10mm but less than 15mm, disease documented by indirect evidence only (e.g., lab values) or previously radiated lesions that have not progressed.

Target lesions are defined as all measurable lesions up to a maximum of 2 lesions per organ, 5 lesions in total, representative of all involved organs and should be identified as target lesions at baseline. Target lesions should be selected on the basis of size (lesions with longest diameter for non-lymph nodes and nodes with longest short axis  $\geq 15\text{mm}$ )

and suitability for accurate repeated measurements. Measurements are recorded in mm and must be provided for target lesions.

Non-target lesions may include non-measurable disease lesions and measurable lesions not identified as target lesions. Absent, indeterminate, present/not increased or increased are the evaluation codes for non-target disease assessment.

Inadequate tumor assessment does not allow for a RECIST response determination and will be designated as Not Evaluable target response evaluation. An inadequate assessment will be defined as those with at least 1 missing measurement or non-measurable target lesion or baseline tumor assessment outside the screening evaluation window (i.e., after first dose date, prior to -28 days from first dose date). If a target lesion is too small to measure and does not have unequivocal complete disappearance, a default of 5mm will be assigned.

Different imaging of lesions should not be performed. Imaging variations that result in PR or CR based on the inconsistency of imaging will be reviewed carefully and may result in adjudication. Response is assessed in EDC by investigators with documented (objective) status at each assessment.

Objective review of tumor assessment scans will be performed using both investigator assessments and central review. Central review will be generated per an imaging service charter. Central review will be conducted independently of investigator assessment responses.

Table 1 Definitions of Target and Non-Target Response per RECIST version 1.1

Objective Response	Target Lesions	Non-Target Lesions
Complete Response (CR)	Disappearance of all target lesions. All pathological lymph nodes must have decreased to < 10 mm on the short axis.	Disappearance of all non-target lesions. All lymph nodes must be non-pathological in size (i.e., <10 mm short axis). Normalization of tumor marker levels
Partial Response (PR)	At least a 30% decrease in the sum of the longest diameters (SLD) of the target lesions, taking the baseline SLD as reference.	Not Applicable
Non-CR / Non-PD	Not Applicable	Persistence of one or more non-target lesion(s) and/or maintenance of tumor marker level above the normal limits

Objective Response	Target Lesions	Non-Target Lesions
Stable Disease (SD)	Neither sufficient shrinkage to qualify as a PR nor an increase for PD.	Not Applicable
Progressive Disease (PD)	SLD increased by at least 20% from the smallest value on study (including baseline, if that is smallest). The SLD must also demonstrate an absolute increase of at least 5 mm.	Unequivocal progression of existing non-target lesions.
Not Evaluable (NE)	Progression not documented and 
 
• <math>\geq 1</math> target lesion not assessed, or
 
• assessment methods inconsistent from baseline, or
 
• <math>\geq 1</math> target lesions cannot be measured accurately (poor visibility)
 
• <math>\geq 1</math> target lesions were excised or irradiated and have not reappeared or increased
 
	Progression has not been determined and $\geq 1$ non-target lesions were not assessed or were inconsistent with those used at baseline
Not Applicable (NA)	set value for all post-baseline disease assessments only if no target lesions are identified at baseline	set value for all post-baseline disease assessments only if no non-target lesions are identified at baseline

Table 2 Response Evaluation per RECIST version 1.1

Target Lesions	Non-Target Lesions	New Lesions	Overall Response
CR	CR or NA	No	CR
CR	Non-CR/Non-PD or NE	No (or NE)	PR
PR	CR or Non-CR/Non-PD or NE or NA	No (or NE)	PR
SD	CR or Non-CR/Non-PD or NE or NA	No (or NE)	SD
PD	Any	Any	PD
Any	PD	Any	PD
Any	Any	Yes	PD
NE	CR or Non-CR/Non-PD or NE or NA	No	NE
NA	CR	No	CR
NA	Non-CR/Non-PD	No	SD

Target Lesions	Non-Target Lesions	New Lesions	Overall Response
NA	NE or NA	No (or NE)	NE
NA	CR or Non-CR/Non-PD	NE	SD

### 8.3.2 OBJECTIVE RESPONSE RATE – INVESTIGATOR ASSESSED AND CENTRAL REVIEW

Objective response rate (ORR) is defined as the proportion of subjects with a Best Overall Response (BOR) characterized as either a Complete Response (CR) or Partial Response (PR) as defined by RECISTv1.1 guidelines, relative to the total number of evaluable subjects in the population of interest. Per RECISTv1.1 guidelines, subjects with documented PR or CR will need confirmatory tumor assessments to document tumor response. Subjects without baseline tumor assessments will be considered non-evaluable for this analysis. Responses are only considered if they occur prior to objective progression and the start of subsequent anticancer therapy.

### 8.3.3 BEST OVERALL RESPONSE – INVESTIGATOR ASSESSED AND CENTRAL REVIEW

Best overall response is defined as the best response (in the order of CR, PR, SD, PD, and NE) among all overall responses recorded from the first dose date until documented PD, or the last evaluable disease assessment in the absence of PD prior to the initiation of subsequent anticancer therapy or end of the study, whichever occurs first. Best Overall Response (BOR) is based on RECIST v1.1 criteria. Subjects with documented PR or CR will need confirmatory tumor assessments to document response (refer to Table 3). If a CR is pending confirmation and is designated at an assessment followed by 1 or more NE, CR may be confirmed thereafter. Similarly, if a PR is pending confirmation and is designated at an assessment followed by 1 or more NE and/or SD assessments, PR may be confirmed thereafter.

Table 3 Best Overall Response

Overall Response First Time Point	Overall Response Subsequent Time Point	Best Overall Response
CR	CR	CR
CR	PR	SD, PD or PR 
CR	SD	SD provided minimum criteria for SD duration met, otherwise, PD
CR	PD	SD provided minimum criteria for SD duration met, otherwise, PD
CR	NE	SD provided minimum criteria for SD duration met, otherwise, NE
PR	CR	PR
PR	PR	PR
PR	SD	SD
PR	PD	SD provided minimum criteria for SD duration met, otherwise, PD
PR	NE	SD provided minimum criteria for SD duration met, otherwise, NE
NE	NE	NE

If a CR is truly met at first time point, then any disease seen at a subsequent time point, even disease meeting PR criteria relative to baseline, makes the disease PD at that point (since disease must have reappeared after CR). Best response would depend on whether minimum duration for SD was met. However, sometimes 'CR' may be claimed when subsequent scans suggest small lesions were likely still present and in fact the patient had PR, not CR at the first time point. Under these circumstances, the original CR should be changed to PR and the best response is PR.

#### 8.3.3.1 CONFIRMED OVERALL RESPONSE

Confirmed overall response is defined as subjects with a best overall response of confirmed CR or confirmed PR that occur prior to the initiation of subsequent anticancer treatment or prior to discontinuation of treatment (due to any other reason), whichever is earlier.

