7.4. End of Treatment (All Parts)

At the end of treatment (within 28 days \pm 7 days after last dose of study drug):

- Physical examination.
- Vital signs.
- ECOG performance status.
- 12-lead ECG.
- Laboratory assessments including chemistry, hematology, coagulation, thyroid function, and urinalysis.
- Prostate cancer subjects in Parts E and F only:
 - PSA
- Blood samples for Target Engagement, PK/ADA/NAb (not required for Part C subjects receiving nivolumab or pembrolizumab post-progression).
- CT Scan for response assessment (unless performed within 9 weeks of End of Treatment visit [within 12 weeks for prostate cancer subjects]).
- Record concomitant medications.
- Adverse events assessment.

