### **8.3.5 PROGRESSION-FREE SURVIVAL – INVESTIGATOR ASSESSED AND CENTRAL REVIEW**

The investigator will make tumor assessments and a separate independent central review will also be performed. All PFS calculations (months) will be the following:

$$[\text{Progression/Death/Censor Date} - \text{First Dose Date} + 1] / 30.4375.$$

PFS is defined as the number of months from the date of first dose to the date of death or documented (objective) disease progression via RECISTv1.1, whichever occurs earliest. Subjects that do not experience progression or death at the time of analysis will have time to progression censored at the date of last valid tumor assessment, which is defined as an overall response other than "not evaluable". The actual tumor assessment date (i.e., scan) will be used, not the reading date of the scan/assessment. If the tumor assessment is performed over multiple days for a documented disease progression, the first date will define the assessment date. If the subject is censored, the last date will define the assessment date. Again the "assessment date" will be defined as the "scan date" and not the overall response date. Tumor assessments are performed within 10 days prior to every 3rd cycle starting from cycle 4 (e.g., C4, C7, C10, etc.) until treatment discontinuation. Subjects discontinuing treatment due to reasons other than documented disease progression will have their tumor assessed (using the same modality that was used during study treatment) every 12 weeks ( $\pm$  2 weeks) for up to 2 years after the last treatment visit, until a) they start a new therapy for their cancer, b) death, c) withdrawal of consent, d) are lost to follow-up, e) the Sponsor notifies sites that tumor assessment is no longer required during long-term follow-up, or f) termination of study by the Sponsor.

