### 8.3.9 IMMUNE-RELATED OBJECTIVE RESPONSE RATE – CENTRAL REVIEW

Immune-related best overall response (irBOR) will only be evaluated according to central review. The irBOR (as defined by irRC guidelines) is recorded from first dose date until documented disease progression (irPD) or death. The irORR is defined as the proportion of subjects with an irBOR characterized as either a confirmed complete response (irCR) or confirmed partial response (irPR) prior to the initiation of subsequent anticancer treatment or prior to discontinuation of treatment (due to any other reason), whichever is earlier; irORR will be calculated relative to the total number of evaluable subjects. Subjects without baseline tumor assessments will be considered non-evaluable for this analysis.

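### Treatment discontinuation ends response counting for confirmed response and irORR but not for ORR and BOR, so responder sets can differ because of the cut-off alone

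*SAP*

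**What the plan says.** Four SAP definitions decide who is a responder.

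- **ORR (8.3.2):** "Responses are only considered if they occur prior to objective progression and the start of subsequent anticancer therapy".
- **BOR (8.3.3):** the best response from first dose until objective progression is recorded; the window has an alternative end, worded as follows: "or the last evaluable disease assessment in the absence of PD prior to the initiation of subsequent anticancer therapy or end of the study". Confirmation of CR and PR is required, and ORR is built on BOR.
- **Confirmed overall response (8.3.3.1):** the confirmed CR or PR must occur before new anticancer treatment "or prior to discontinuation of treatment (due to any other reason), whichever is earlier".
- **irORR (8.3.9):** the confirmed irCR or irPR must occur "prior to the initiation of subsequent anticancer treatment or prior to discontinuation of treatment (due to any other reason), whichever is earlier".

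Scanning does not end with treatment. SAP 8.3.5 states: "Subjects discontinuing treatment due to reasons other than documented disease progression will have their tumor assessed". This continues every 12 weeks (± 2 weeks) for up to 2 years, and Protocol 7.5 agrees. Protocol 7.4 adds an end-of-treatment CT unless one was done within the previous 9 weeks (12 for prostate cancer).

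Confirmed CR or PR is also the first criterion for DCR (SAP 8.3.4) and defines the DOR population (SAP 9.11.3). DOR takes its censoring from SAP 8.3.5.2 (see SAP 8.3.6).

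**The concern.** Two definitions end at treatment discontinuation and two do not, and no section says which prevails. A subject who stops without progression and has a qualifying scan in follow-up can be a responder in one table and a non-responder in another.

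Three things are at stake. First, irORR and RECIST ORR would differ partly because they use different observation windows, so the comparison would no longer isolate the effect of the response criteria. Second, DOR could be summarised for a different set of subjects from those counted in ORR. Third, response rate heads the Phase 2 primary efficacy objective (SAP 3.1.4) and drives the expansion rule in SAP 9.12, so it should be clear which responses count.

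**Working it through.** **1. The cut-offs side by side**

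| Endpoint | Progression | New anticancer therapy | Stopping treatment without progression |
|---|---|---|---|
| ORR (8.3.2) | yes | yes | no |
| BOR (8.3.3) | yes | yes (also end of study) | no |
| Confirmed response (8.3.3.1) | through BOR | yes | **yes** |
| irORR (8.3.9) | irPD or death | yes | **yes** |

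**2. Can the conflicting case arise?** Take a q3w subject with a week-9 scan and a last dose at week 12, who stops for toxicity.

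- The end-of-treatment visit falls at week 12 + 4 = 16 (15 to 17 with the ± 7 days). That is 16 − 9 = 7 weeks (6 to 8) after the last scan, under 9 weeks, so no CT is required.
- The first follow-up scan is due at week 12 + 12 = 24 (22 to 26).

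Both cases below assume no progression, no new therapy, and shrinkage large enough for both RECIST PR and irPR.

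- *Case A:* PR at week 9, PR again at week 24. The gap is 24 − 9 = 15 weeks, which meets the 4-week irRC minimum.
- *Case B:* stable at week 9, first PR at week 24, PR again at week 36.

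| | ORR and BOR | Confirmed response and irORR |
|---|---|---|
| A, clause applies to first response | counts | counts |
| A, clause applies to confirming scan | counts | **excluded** |
| B, either reading | counts | **excluded** |

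The clause can only remove responders. It can lower irORR relative to what the ORR cut-off would give, and never raise it. The observed sign of ORR minus irORR also depends on the criteria themselves.

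**3. Duration of response.** SAP 8.3.6 uses (censor date − first response date + 1)/30.4375. For discontinuation due to toxicity or other reasons, SAP Table 4 censors at the last assessment without PD before discontinuation. That is week 9, or day 63 counted from first dose; week 24 is day 168.

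- Case B: (63 − 168 + 1)/30.4375 = −104/30.4375 = −3.4 months.
- Case A: (63 − 63 + 1)/30.4375 = 0.03 months, one day, although the subject is still in PR 15 weeks later.

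The bulleted text of 8.3.5.2 does not limit the last assessment to the period before discontinuation; Table 4 does.

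**4. Size if 8.3.3.1 governs RECIST ORR.** Clopper-Pearson 95% intervals for a 15-subject cohort:

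- 0/15 = 0% (0 to 21.8)
- 1/15 = 6.7% (0.2 to 31.9)
- 2/15 = 13.3% (1.7 to 40.5)

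With 15 subjects, the Table 9 boundary is 0: no responses means stop, one or more means expand. Moving from 1 to 0 crosses it; moving from 2 to 1 does not.

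The documents give no rate for responses that depend on post-treatment scans. As an assumption only, let a fraction q of responses be lost this way, with a true ORR of 20% (the SAP 9.12 alternative). Then P(0 of 15) = (1 − 0.20(1 − q))^15:

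| q | Counted ORR | P(0 of 15) |
|---|---|---|
| 0 | 20% | 3.5% |
| 10% | 18% | 5.1% |
| 20% | 16% | 7.3% |
| 30% | 14% | 10.4% |

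**The case against.** The best defence is that 8.3.3.1 sits beneath BOR and was meant as an on-treatment rule for every response endpoint. RECIST ORR and irORR would then share a cut-off, which would also fit the Table 4 censoring. This is a tenable design, but 8.3.2 and 8.3.3 set a wider window, and neither they nor SAP 9.11.1 refers to 8.3.3.1.

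A reader might infer that RECIST ORR is biased downward. The documents do not support that as it stands: on its own wording, ORR loses nobody. ORR bias and an ORR/irORR mismatch need opposite readings, so they cannot both be asserted. Confirmed overall response is not in the endpoint list of SAP 3.2.3; the only listed response rate expressly cut at discontinuation is irORR.

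A reader might also take Case A as certain. It depends on whether the clause refers to the first response or the confirming scan. SAP 8.3.6 dates a response from first documentation, which favours the first; Case B survives either way.

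Other limits also stand. Nothing in the documents shows that stopping for toxicity while responding is common, only that it is foreseeable (Protocol Table 5 requires permanent discontinuation for several immune toxicities). DCR is largely protected, because an unconfirmed CR or PR lasting 53 days (9 × 7 − 10) counts. The expansion rule is permissive, and SAP 3.3.1 disclaims formal testing. The sponsor may end follow-up scanning, and central reading of those scans depends on an imaging charter that is not among the documents.

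**Conclusion.** The inconsistency is in the current text and the scan schedule makes it operative. A response first seen after stopping without progression counts in ORR but not in confirmed response or irORR. A response confirmed after stopping joins it if the clause is tied to the confirming scan. irORR is understated relative to ORR by the cut-off whenever such a case occurs, and the DOR responders can differ from the ORR responders.

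A downward bias in RECIST ORR is conditional on 8.3.3.1 governing it. Only then does one subject in 15 (6.7 points) matter at the expansion rule, and only when that subject is the sole responder. No expected size can be given, since the documents state no frequency; the 10% to 30% range above is illustrative.

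**What to change.** - Delete "or prior to discontinuation of treatment (due to any other reason), whichever is earlier" from 8.3.3.1 and 8.3.9.
- Use one cut-off for ORR, confirmed response, irORR and the DOR responder set: progression (irPD for irRC) or new anticancer therapy.
- State whether the cut-off applies to the date of first response or to the confirming scan.
- For DOR, replace the Table 4 rule that censors at the last assessment before discontinuation with censoring at the last evaluable assessment before progression or new therapy. Without this change, responses first seen after stopping enter DOR with negative durations, as in Case B.

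The cost is a revised SAP with the further signatures that SAP Section 2 requires, and a little extra programming. No new scans are needed beyond those scheduled, but the sponsor should confirm that the imaging charter covers central reads of post-treatment scans. The downside is that some counted responses will rest on scans taken after treatment ended.

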#### 8.3.4 DISEASE CONTROL RATE – INVESTIGATOR ASSESSED AND CENTRAL REVIEW

Disease control rate (DCR) is defined as the ratio of subjects having any of the following response:

- Confirmed CR or PR; Or
- BOR of SD (or unconfirmed CR or PR) lasting at least 53 days (9 weeks less 10 days) from date of first dose.

Note that a SD at the first scan requires a follow-up scan of SD or better (PR or CR) along with the timeframe requirement. Unconfirmed responses will be considered SD at study completion.

### **8.3.5 PROGRESSION-FREE SURVIVAL – INVESTIGATOR ASSESSED AND CENTRAL REVIEW**

The investigator will make tumor assessments and a separate independent central review will also be performed. All PFS calculations (months) will be the following:

$$[\text{Progression/Death/Censor Date} - \text{First Dose Date} + 1] / 30.4375.$$

PFS is defined as the number of months from the date of first dose to the date of death or documented (objective) disease progression via RECISTv1.1, whichever occurs earliest. Subjects that do not experience progression or death at the time of analysis will have time to progression censored at the date of last valid tumor assessment, which is defined as an overall response other than "not evaluable". The actual tumor assessment date (i.e., scan) will be used, not the reading date of the scan/assessment. If the tumor assessment is performed over multiple days for a documented disease progression, the first date will define the assessment date. If the subject is censored, the last date will define the assessment date. Again the "assessment date" will be defined as the "scan date" and not the overall response date. Tumor assessments are performed within 10 days prior to every 3rd cycle starting from cycle 4 (e.g., C4, C7, C10, etc.) until treatment discontinuation. Subjects discontinuing treatment due to reasons other than documented disease progression will have their tumor assessed (using the same modality that was used during study treatment) every 12 weeks ( $\pm$  2 weeks) for up to 2 years after the last treatment visit, until a) they start a new therapy for their cancer, b) death, c) withdrawal of consent, d) are lost to follow-up, e) the Sponsor notifies sites that tumor assessment is no longer required during long-term follow-up, or f) termination of study by the Sponsor.

